2.6.4 Supportive Analyses for key secondary estimand

2.6.4.1 Sensitivity analyses for key secondary estimand

First sensitivity analysis estimand: The target population, the primary variable, the treatment of interest, intercurrent events, and the summary measure of this endpoint are the same as those for the key secondary estimand. To assess the impact of stratification, the two treatment arms will be compared using the unstratified log-rank test. In the summary tables, this approach is referred to as '*unstratified OS sensitivity analysis*'.

Second sensitivity analysis estimand: the target population, the primary variable, the treatment of interest, intercurrent events, and the summary measure of this endpoint are the same as those for the key secondary estimand. The two treatment arms will be compared using the stratified log-rank test with stratification factors derived from the clinical database. In the summary tables, this approach is referred to as '*OS sensitivity analysis with stratification factors from eCRF*'.

2.6.4.2 Supplementary analyses for key secondary estimand

First supplementary analysis estimand: the target population, the primary variable, the treatment of interest, and intercurrent events are the same as those for the key secondary estimand. A Cox regression model, stratified by randomization stratification factors, will be fitted to evaluate the effect of the baseline demographic and disease characteristics, which include age (< 50 years vs. (\geq 50 years and < 65 years) vs. (\geq 65 years and < 75 years) vs. \geq 75 years), gender (Male vs. Female), race (White vs. Black vs. Asian vs. Others (includes "Native Hawaiian or Other Pacific Islander" and "American Indian or Alaska Native")), ECOG status (0 vs. \geq 1), and smoking history (never vs. former smoker vs. current smoker). In the summary tables, this approach is referred to as '*OS supplementary analysis adjusted for baseline covariates*'.

Second supplementary analysis estimand: In addition, analysis to assess the treatment effect based on OS, had COVID-19 pandemic not occurred, will be conducted. The target population, treatment of interest, and the summary measure of this endpoint are the same as those for the key secondary estimand. The variable is defined as the time from the date of randomization to the date of death due to non-COVID-19 pandemic reasons. The remaining intercurrent events will be handled as follows:

- **Discontinuation of study treatment due to any non-COVID-19 pandemic reasons:** OS will take into account all deaths and assessments, irrespective of the study treatment discontinuation reasons (treatment policy)
- **Discontinuation of study treatment due to COVID-19 pandemic reasons:** OS will be censored on the date of discontinuation of treatment due to COVID-19 pandemic (hypothetical strategy). The discontinuation reason due to COVID-19 pandemic will be identified from the defined COVID-19 protocol deviations.
- **Medications used for treating suspected or confirmed COVID-19 cases:** OS will be censored on the date of administration of COVID-19 medication (hypothetical strategy). Details to identify medications are shown in [Section 2.5.4.2.1](#)
- **Death due to COVID-19:** OS will be censored on the date of death due to COVID-19 (hypothetical strategy)

In the summary tables, this approach is referred to as ‘COVID-19 OS supplementary analysis’.

2.6.4.3 Subgroup analyses for key secondary estimand

If the key secondary efficacy analysis is *statistically significant*, OS will be summarized for the subgroups specified in [Section 2.2.1](#):

- Median OS with its 95% CI from Kaplan-Meier estimation of the OS distribution
- Hazard ratio with its 95% CI using Cox proportional hazards model stratified by randomization stratification factors

A forest plot, including sample size, number of events, and HR with its 95% CI, will be produced for subgroups. *p*-values will not be generated.

2.7 Analysis of secondary efficacy objectives

Along with the OS as the key secondary endpoints, three secondary efficacy objectives are also evaluated:

- To compare DFS by local investigator assessment and OS in the canakinumab versus placebo arms in subgroups defined by PD-L1 expression levels
- To compare DFS by local investigator assessment and OS in the canakinumab versus placebo arms in subgroups defined by CD8 expression levels
- To compare lung cancer-specific survival (LCSS) in the canakinumab arm versus placebo arm is an important secondary efficacy objective.

2.7.1 Secondary endpoints

In order to evaluate the effect of canakinumab within PD-L1 subgroups, DFS and OS analyses will be performed by PD-L1 subgroups with 1% cut-off on tumor cells (TC) to define positive or negative status as determined by IHC (<1% and ≥1%). Additionally, PD-L1 subgroups will also be assessed using ≥ 50% cut-off (<50% and ≥50%). A comparison between <1%, ≥1-49%, and ≥ 50% PD-L1 expression level subgroups will also be done.

In order to evaluate the effect of canakinumab within CD8 subgroups, DFS and OS analyses will be performed by CD8 subgroups with the median and quartiles (including quartile-complements, e.g.

below lower quartile and above lower quartile) of baseline CD8 as cut-offs. In addition, the relation between CD8 expression in resected tumor sample and clinical outcome will be evaluated using CD8 as continuous, potentially log-transformed, co-variate as well as categorical covariates in a Cox model. These analyses will support the establishment of CD8 as a prognostic/predictive factor if there is an expression level correlating to clinical outcome regardless of treatment (prognostic) and/or associated with canakinumab treatment (predictive).

LCSS is a secondary efficacy endpoint, defined as the time from the date of randomization to the date of death due to lung cancer. For subjects who have died due to reasons other than lung cancer, LCSS will be censored at the death date. For subjects who is not known to have died, LCSS will be censored at the last date the subject was known to be alive (on or before the cut-off date); they will be censored for 'Lost to follow-up' if the time between their last contact date and the analysis cut-off date is longer than 14 weeks, i.e., the protocol specified interval between the survival follow-up assessments plus 2 weeks.

The LCSS distribution will be estimated using the Kaplan-Meier method. Kaplan-Meier curves, medians and its 95% CI will be presented for each arm. The HR and its 95% CI for LCSS will be calculated using a stratified Cox model. The number of censored subjects will be summarized by treatment. Reasons for censoring ('Alive', 'Lost to follow-up', 'Death due to reasons other than lung cancer'), along with death cause, will be summarized and listed by treatment.

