10.5.2 Other secondary efficacy objectives

In order to evaluate the effect of canakinumab within PD-L1 subgroups, DFS and OS analyses will be performed by PD-L1 subgroups with 1% cut-off on tumor cells (TC) to define positive or negative status as determined by IHC. Additionally, PD-L1 subgroups will also be assessed using \geq 50% cut-off. Therefore, a comparison between <1%, \geq 1-49%, and \geq 50% PD-L1 expression level subgroups will be done.

In order to evaluate the effect of canakinumab within CD8 subgroups, DFS and OS analyses will be performed by CD8 subgroups with the median and quartiles (including quartile-complements, e.g. below lower quartile and above lower quartile) of baseline CD8 as cut-offs. In addition, the relation between CD8 expression in resected tumor sample and clinical outcome will be evaluated using CD8 as continuous, potentially log-transformed, co-variate as well as categorical covariates in a Cox model. These analyses will support the establishment of CD8 as a prognostic/predictive factor if there is an expressions level correlating to clinical outcome.

Lung cancer specific survival (LCSS) is defined as the time from the date of randomization to the date of death due to lung cancer. Analyses will be based on the FAS population according to the randomized treatment group and strata assigned at randomization. The LCSS distribution will be estimated using the Kaplan-Meier method, and Kaplan-Meier curves, medians and 95% confidence intervals of the medians will be presented for each treatment group. The hazard ratio for LCSS will be calculated, along with its 95% confidence interval, using a stratified Cox model.

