The primary endpoint was not met for this study as described in the [[CACZ885T2301 Primary Analysis CSR](#)]; therefore, no formal statistical analysis will be performed for this close-out CSR. The outputs for the close-out CSR consist mainly of summary tables prepared using descriptive statistics as well as data listings.

2 Planned tables, figures and listings

The table below provides the list of outputs that need to be generated, with additional guidelines added under 'Notes'. Please follow the in-text layout given below, post-text output has been added for reference.

Add footnote: CACZ885T2301- *Cut-off date*: 07Feb2023

Output Number in close-out CSR	Output title in close-out CSR	Output number in primary CSR	Output title in primary CSR	Notes
Table 2-1	Subject disposition (Full analysis set)	Table 10-1	Subject disposition (Full analysis set)	
Table 2-2	Protocol deviation ($\geq 0.4\%$ for any treatment arm) (Full analysis set)	Table 10-2	Protocol deviation ($\geq 0.4\%$ for any treatment arm) (Full analysis set)	
Table 2-3	Duration of exposure to study drug (Safety set)	Table 10-7	Duration of exposure to study drug (Safety set)	
Table 2-4	Dose of study drug received (Safety set)	Table 10-8	Dose of study drug received (Safety set)	
Table 2-5	Dose interruptions and discontinuation of study drug (Safety set)	Table 10-9	Dose interruptions and discontinuation of study drug (Safety set)	
Table 2-6	Summary of overall survival by study arm (Full analysis set)	Table 11-3	Summary of overall survival by study arm (Full analysis set)	

Table 2-6a	Summary of overall survival by study arm and baseline PD-L1 subgroup (Baseline PD-L1: < 1% vs. ≥ 1%) (Full analysis set)	Table 11-3a	Summary of overall survival by study arm and baseline PD-L1 subgroup (Baseline PD-L1: < 1% vs. ≥ 1%) (Full analysis set)	
Table 2-6b	Summary of overall survival by study arm and baseline PD-L1 subgroup (Baseline PD-L1: < 1% vs. ≥ 1% and < 49% vs. ≥ 50%) (Full analysis set)	Table 11-3b	Summary of overall survival by study arm and baseline PD-L1 subgroup (Baseline PD-L1: < 1% vs. ≥ 1% and < 49% vs. ≥ 50%) (Full analysis set)	
Table 2-6c	Summary of overall survival by study arm and baseline PD-L1 subgroup (Baseline PD-L1: < 50 % vs. ≥ 50%) (Full analysis set)	Table 11-3c	Summary of overall survival by study arm and baseline PD-L1 subgroup (Baseline PD-L1: < 50 % vs. ≥ 50%) (Full analysis set)	

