2.2.1 Subgroup of interest

Efficacy

The primary endpoint (DFS) and key secondary endpoint (OS) will be summarized by the following subgroups to examine homogeneity of treatment effect, provided that the corresponding primary efficacy analysis and key secondary efficacy analysis based on the FAS are statistically significant respectively:

- AJCC/UICC v. 8 stage (IIA vs. IIB vs. IIIA vs. IIIB with T>5cm, N2 disease) based on randomization data from IRT
- AJCC/UICC v. 8 stage (IIA vs. IIB vs. IIIA vs. IIIB with T>5cm, N2 disease) based on eCRF data
- Histology (squamous vs. non-squamous) based on randomization data from IRT

- Histology (squamous vs. non-squamous) based on eCRF data
- Region (Western Europe and North America vs. eastern Asia vs. Rest of the world (RoW)) based on randomization data from IRT
- Sex (Male vs. Female)
- Race (White vs. Black vs. Asian vs. Others (includes “Native Hawaiian or Other Pacific Islander” and “American Indian or Alaska Native”))
- Age category (<50 years vs. (≥50 years and <65 years) vs. (≥65 years and <75 years) vs. ≥75 years)
- ECOG PS status (0 vs. ≥ 1)
- Smoking history (never vs. former smoker vs. current smoker)

█ [REDACTED]

█ [REDACTED]

- EGFR mutant status (mutant vs. non-mutant) based on *local* testing during screening
- Prior chemotherapy (yes vs. no) in subjects with stage IIA and N0 disease based on eCRF data
- Prior radiotherapy (yes vs. no) in subjects with N2 disease based on eCRF data
- PD-L1 categories (<1%, ≥ 1 %, < 50%, ≥ 50%, ≥ 1 % and < 49%)
- CD8 categories by median or quartile (including its complements)

No formal statistical test of hypotheses will be performed for the subgroups. Kaplan-Meier method will be used for summarizing medians and their corresponding 95% C.I. of DFS or OS. Hazard ratio (HR) for the treatment effect and its 95% confidence intervals will be summarized based on Cox regression model stratified by randomization stratification factors. The objective of the efficacy subgroup analysis is to demonstrate homogeneity of treatment effect in the above subgroups.

Safety

Key safety analyses, including AEs and AESIs, will be repeated on safety set in the following subgroups:

- Sex (Male vs. Female)
- Race (White vs. Black vs. Asian vs. Others (includes “Native Hawaiian or Other Pacific Islander” and “American Indian or Alaska Native”))
- Age category (<50 years vs. (≥50 years and <65 years) vs. (≥65 years and <75 years) vs. ≥75 years)
- ECOG PS status (0 vs. ≥ 1)

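### In readable text, the plan aims to support CD8 as predictive of canakinumab benefit but names no direct estimate of how the treatment effect changes with CD8; separately, a <49% limit drops a PD-L1 value of 49% from the three-way split

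*SAP*

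**What the plan says.** **CD8.** Protocol 10.5.2 sets the aim: "These analyses will support the establishment of CD8 as a prognostic/predictive factor". SAP 2.7.1 spells out the two senses: an expression level "correlating to clinical outcome regardless of treatment (prognostic) and/or associated with canakinumab treatment (predictive"). Both documents name two tools:

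- DFS and OS analyses within subgroups cut at the CD8 median and quartiles, including quartile complements.
- CD8 as a continuous, possibly log-transformed, "co-variate as well as categorical covariates in a Cox model". The model's other terms are not listed.

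SAP 2.2.1 gives hazard ratios with 95% CIs within subgroups and adds: "No formal statistical test of hypotheses will be performed for the subgroups". SAP 2.5.5 and 2.6.4.3 add forest plots without p-values. The only model interaction in the readable SAP is treatment by time, for patient-reported outcomes (2.11 and 5.5).

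**PD-L1.** SAP 2.7.1 says: "A comparison between <1%, ≥1-49%, and ≥ 50% PD-L1 expression level subgroups will also be done". Protocol 10.5.2 uses the same bands. The SAP 2.2.1 efficacy list reads "PD-L1 categories (<1%, ≥ 1 %, < 50%, ≥ 50%, ≥ 1 % and < 49"%); the safety list in 2.2.1 and the baseline list in 2.3 match it. Close-out SAP Tables 2-6b and 14.2-2.1b carry the title "Baseline PD-L1: < 1% vs. ≥ 1% and < 49% vs. ≥ 50"%.

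**Gate.** SAP 2.2.1 makes its efficacy subgroup list, which includes PD-L1 and CD8, conditional: "provided that the corresponding primary efficacy analysis and key secondary efficacy analysis based on the FAS are statistically significant respectively". SAP 2.5.5 and 2.6.4.3 repeat the condition. SAP 2.7 and 2.7.1 and Protocol 10.5.2 list the PD-L1 and CD8 comparisons without it.

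**The concern.** A marker is predictive if the treatment effect changes with it. That is a statement about a difference between hazard ratios, and the readable plan names no quantity that measures it: no treatment-by-CD8 term, no ratio of subgroup hazard ratios. The CD8 coefficient in a covariate model describes outcome averaged over the arms. The subgroup hazard ratios do bear on the question, but the reader must compare them by eye, without an interval for the difference. The risk is over-reading a secondary biomarker result in either direction.

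The PD-L1 limit is a different kind of problem: the same three-way split is defined in two ways, and one of them omits a value.

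**Working it through.** **1. Check of the approximation.** Inputs from Protocol 10.7.1 and 10.8: 392 DFS events, HR 0.716 (log HR -0.334), 1:1 allocation, one-sided 2.5%, futility bound Z = 0.226 at 196 events, final bound Z = 1.969. With SE(log HR) = 2/√events, single-look power is Φ(0.334 × √392/2 - 1.96) = Φ(1.347) = 91.1%. Two-look power, P(Z₁ > 0.226 and Z₂ > 1.969) with correlation √0.5, is 90.5%. The plan states 90.4%, so the SE formula can be used below.

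**2. Ratio of the two median-half hazard ratios.** Assume 196 events per half and CD8 known for every event.

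- SE = √(4/196 + 4/196) = 0.202.
- The 95% CI is the estimate times or divided by exp(1.96 × 0.202) = 1.49. This does not depend on the true HR.
- Power for a ratio of 0.716 (chosen to equal the planned HR) = Φ(0.334/0.202 - 1.96) = 38%.

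**3. Continuous log CD8.** Assume log CD8 is normal and the effect linear.

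- Interaction SE per SD = 2/√392 = 0.101.
- The means of the two halves differ by 2√(2/π) = 1.596 SD, so the SE on the half-versus-half scale is 0.161 and the CI factor is exp(1.96 × 0.161) = 1.37.
- Power = Φ(0.334/0.161 - 1.96) = 54%. The median split loses 1 - 2/π = 36% of the information.
- If only 70% of events have a CD8 value (an assumption; 274 events), power is 28% (split) and 41% (continuous). For OS at the planned 318 deaths it is 32% and 46%.

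**4. How far by-eye comparison can mislead.** Suppose the true HR is the same in both halves. With SE = 2/√196 = 0.143, let p be the chance that one half's 95% CI excludes 1. The chance that exactly one does is 2p(1 - p).

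| True HR in both halves | p | Exactly one half excludes 1 |
|---|---|---|
| 0.716 | 0.647 | 46% |
| 0.9 | 0.114 | 20% |
| 1 | 0.05 | 9.5% |

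**5. What each quantity can separate.** Simulation with 3,000 runs per scenario: 1382 subjects, cut at DFS event 392, placebo median 48 months, uniform entry over 40 months, 5% yearly dropout, 24 randomization strata (proportions and stage effects assumed), stratified Cox. In A, CD8 acts only through canakinumab (interaction -0.209 per SD). In B, it is purely prognostic (-0.0925 per SD), sized to match A's main effect.

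| | A | B |
|---|---|---|
| CD8 main-effect HR per SD (nominally significant) | 0.915 (41%) | 0.911 (44%) |
| Median-half HRs | 0.61 and 0.85 | 0.72 and 0.72 |
| CI for ratio of half HRs excludes 1 | 36% | 5% |
| CI for interaction excludes 1 | 52% | 5% |

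A second simulation (200 runs, about 350 events) agrees. An interaction of -0.30 with no main effect gave a covariate-only CD8 coefficient of about -0.14, and a prognostic effect of -0.15 gave about -0.15. Adding the interaction term recovered -0.30 and about 0.

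**6. PD-L1 bands.** Each whole percent from 0 to 100 was assigned under each definition.

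- Close-out Tables 2-6b and 14.2-2.1b: 49 is the only whole percent in no band.
- SAP 2.2.1 and 2.3 lists: 49 is inside ≥1% and <50%, so it is missing only from the three-way split.
- SAP 2.7.1 and Protocol 10.5.2: 49 is in the middle band.
- Middle band written as ≥1% and <50%: no value is left out.

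**The case against.** The strongest case is that the CD8 plan is incomplete in wording rather than wrong. The stated objective is to compare arms within CD8 subgroups, and that is fully specified. The aim is modest: the analyses support a role for CD8 if there is a level that correlates with outcome. The ratio of half hazard ratios can be computed from what is reported, and step 5 shows the planned half hazard ratios do differ between the two scenarios. Scenario B was sized so that the main effects would match. All of this stands. A reader might infer that the plan cannot address prediction at all; the documents do not support that.

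Nor is absence from the whole plan established. The SAP contents list is blanked between 2.11 and 2.13, and the protocol text passes from 10.5.6 to 10.7. Protocol Table 3-2 refers sub-study biomarker analyses to 10.6.1. A CD8 interaction model may sit in the hidden text.

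A reader might take the 46% as the chance of a false predictive claim. No passage says CD8 will be called predictive when one half's CI excludes 1. The figure also assumes HR 0.716 in both halves, while the close-out SAP reports that the primary endpoint was not met. The range in step 4 is the fair statement.

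A reader might also conclude that 49% falls in no band wherever <49% is written. That holds only for the two close-out tables. Their companion tables, split at 1% and at 50%, include 49%.

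Finally, the gate wording might suggest that OS by PD-L1 and CD8 would go unreported. The close-out SAP lists those tables, with their primary-CSR numbers, despite the missed primary endpoint, so OS reporting is not in doubt.

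**Conclusion.** The point holds as a minor one, within readable text. The predictive half of the CD8 aim has no direct estimate. A CD8 main effect cannot supply one, and the subgroup hazard ratios do so only indirectly. A direct estimate would show how little the data can say: at 392 events the ratio of half hazard ratios is known only to within a factor of about 1.49, or 1.37 with continuous log CD8 if the effect is linear and log CD8 is normal. These figures assume evenly split events and complete CD8 data; incomplete data widen them.

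The PD-L1 limit is a plain inconsistency between the SAP's own sections and with the protocol. Its effect is probably small, but the documents give no count of subjects at 49%.

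The gate conflict is one of wording, plus the OS subgroup forest plot, which SAP 2.6.4.3 makes conditional and the close-out SAP still lists. None of this touches the primary or key secondary conclusions.

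**What to change.** 1. In SAP 2.7.1, state the Cox model's terms: an exploratory model in FAS subjects with a CD8 value, stratified by the randomization factors, with treatment, log CD8 and treatment-by-log CD8, for DFS and for OS. Report the interaction HR with its 95% CI and no formal test. At the least, report the ratio of the median-half hazard ratios with its CI. If SAP 2.12 already holds such a model, a cross-reference is enough.
2. Change <49% to <50% in all five places: both lists in SAP 2.2.1, the list in SAP 2.3, and close-out Tables 2-6b and 14.2-2.1b.
3. Take the PD-L1 and CD8 bullets out of the significance-gated efficacy list in SAP 2.2.1, which 2.5.5 and 2.6.4.3 refer to. Reconcile 2.6.4.3 with the OS forest plot listed for close-out (Figures 2-2 and 14.2-2.2).

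The cost is wording and one model per endpoint, with no new data. The primary CSR already exists and the close-out SAP plans no formal analysis, so a model added now must be labelled post hoc. Power is low, so a null interaction would be inconclusive. There is no multiplicity control across markers and endpoints. The continuous form gains over the median split only if the effect is roughly linear in log CD8.

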1.3.1.2.1 Clinical Safety

Due to the mode of action of all inhibitors of the IL-1 pathway, infections, predominately of the upper respiratory system, are the main risk in subjects treated with canakinumab. Canakinumab is associated with an increased incidence of serious infections during and after treatment. Although the majority of reports of infection resolved spontaneously or with standard therapy, severe, serious and fatal infections have been reported, including reports of fatal complicated perforated diverticulitis and sepsis. Opportunistic infections have also been reported.

Neutropenia has been observed with medicinal products that inhibit IL-1, including canakinumab. Other than neutropenia, thrombocytopenia, and uric acid increase specific for active gouty arthritis, there was no evidence of other clinically relevant drug-related changes in vital signs, electrocardiogram (ECG) or laboratory values (see local label for Ilaris[®]).

Confidential

Both *i.v.* and *s.c.* injections of canakinumab are well tolerated as evidenced by a low rate of injection-site events and discontinuations. Low treatment-related immunogenicity (<3%) has been detected, and no clinical consequences to detected anti-drug antibodies were evident. No apparent impact on canakinumab pharmacokinetics or on total IL-1 β concentration (pharmacodynamics) were evident; or any evidence of immune-related loss of efficacy. Overall, the immunogenicity profile is entirely consistent a cross all disease areas.

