10.5 Secondary objectives

Secondary objectives of the study are as specified in Table 3-1. The secondary objectives in this study are to compare the two treatment groups with respect to overall survival (OS), lung cancer specific survival (LCSS), DFS and OS in PD-L1 and CD8 subgroups, time to 10 point definitive deterioration and first 10 point definitive deterioration in patient-reported outcomes, including key symptom scores, and safety. OS is identified as the key secondary endpoint. A hierarchical testing strategy will be used to control the overall type I error rate, where OS will only be formally tested and interpreted if the primary analysis of DFS is statistically significant.

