10.9 Power for analysis of key secondary variables

OS, as the key secondary variable, will be formally statistically tested, provided that the primary variable DFS is statistically significant. The hypotheses to be tested and details of the testing strategy are provided in Section 10.5.1 and Section 10.7.2. Based on available data, the median OS in the placebo arm is expected to be approximately 5 years (Pignon 2008). In addition, the OS result presented in Kelly (2015) was not mature as the median was not reached at 5 years, but the overall trend indicates a median OS greater than 5 years. After taking these into consideration, the median OS for the placebo arm is assumed to be approximately 66 months. It is hypothesized that treatment with canakinumab will result in a 22.4% reduction in the hazard rate for OS, i.e., an expected hazard ratio of 0.776 (which corresponds to an increase in median 66 to 85 months under the exponential model assumption). Then, in order to ensure 80% power to test the null hypothesis: OS hazard ratio = 1, versus the specific alternative hypothesis: OS hazard ratio = 0.776, it is calculated that a total of 504 deaths need to be observed. This calculation assumes analysis by a one-sided log-rank test at the overall 2.5% level of significance, subjects randomized to the two treatment arms in a 1:1 ratio, and a 3-look group sequential design with a Lan-DeMets (O'Brien-Fleming) a-spending function using information fractions of 63%, 83% and 100%. Based on the same number of subjects that are planned to be enrolled in this study to provide sufficient power for the primary endpoint (i.e., 1500 subjects), and assuming losses to follow-up for OS of 3% yearly, it is estimated that these 504 deaths will be observed approximately 63 months after the randomization date of the first subject. Therefore the cut-off date for the final analysis of OS will be approximately 21 months

after the cut-off date for the final analysis of DFS. These calculations were made using the software package East 6.4.

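### Kaplan-Meier LCSS curves with other-cause deaths censored overstate absolute lung-cancer mortality and can distort absolute arm differences in either direction; cumulative incidence of both causes should be added

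*SAP*

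**What the plan says.** SAP 2.7.1 gives LCSS as "defined as the time from the date of randomization to the date of death due to lung cancer". On competing deaths it says: "For subjects who have died due to reasons other than lung cancer, LCSS will be censored at the death date". Subjects not known to have died are censored when last known alive. Kaplan-Meier curves, medians and 95% confidence intervals follow for each arm, and for the comparison, "The HR and its 95% CI for LCSS will be calculated using a stratified Cox model". The same section lists death from a cause other than lung cancer among the censoring reasons, and says that these reasons, "along with death cause, will be summarized and listed by treatment".

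Protocol 10.5.2 plans the same methods ("The LCSS distribution will be estimated using the Kaplan-Meier method", with a stratified Cox model) but gives no rule for other-cause deaths. No cumulative incidence function or other competing-risk analysis of LCSS appears in the readable text of either document.

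On status, SAP 2.7 singles LCSS out as an important secondary objective, but it has no alpha and no planned test. Protocol 10.5 reserves the formal hierarchy for DFS and then OS: "OS is identified as the key secondary endpoint". The close-out SAP still lists an LCSS summary table and a listing.

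**The concern.** Kaplan-Meier treats a censored subject as someone who could still have the event later. A subject who has died of infection or heart disease cannot. One minus the LCSS Kaplan-Meier curve therefore estimates lung-cancer mortality in a population where nobody dies of anything else. The share of randomized subjects who die of lung cancer is the cumulative incidence, and it is lower whenever any other-cause death occurs.

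This matters here because the documents give reason to expect other-cause death to differ by arm. Protocol 1.3.1.2.1 states: "Canakinumab is associated with an increased incidence of serious infections during and after treatment". Protocol 2.6 reports numerically more infection and sepsis deaths on canakinumab than on placebo in the earlier cardiovascular trial. If other-cause death does differ, an absolute arm difference read from the Kaplan-Meier curves will not match the difference in the proportion who die of lung cancer.

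**Working it through.** **Inputs.** The documents give no LCSS rate, event count or power, so there is no LCSS figure to reproduce. The scale comes from the OS assumptions in Protocol 10.9: "the median OS for the placebo arm is assumed to be approximately 66 months", with OS hazard ratio 0.776 and 504 deaths. Those inputs are consistent with the plan:

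- Median: 66/0.776 = 85.1 months (stated 85).
- Fixed-design power: Φ(√504/2 × |ln 0.776| − 1.96) = 81.2%. The three-look design gives 80.2% (stated 80%).

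Assumed, not from the documents: constant and independent cause-specific hazards, the lung-cancer share *s* of placebo deaths, the ratio *r* of other-cause hazards (canakinumab/placebo), and use of the OS hazard ratio for lung-cancer death.

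**Step 1: overstatement in the placebo arm.** All-cause hazard λ = ln 2/66 = 0.0105 per month. Then:

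- 1−KM = 1 − exp(−sλt)
- cumulative incidence (CIF) = s × (1 − exp(−λt))

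All-cause mortality is 31.5% at 36 months and 46.7% at 60 months. For s = 0.8 at 36 months, 1−KM = 1 − exp(−0.8 × 0.0105 × 36) = 26.1% and CIF = 0.8 × 31.5% = 25.2%.

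| Lung-cancer share | 1−KM, 36 mo | CIF, 36 mo | Excess (points) | 1−KM, 60 mo | CIF, 60 mo | Excess (points) |
|---|---|---|---|---|---|---|
| 90% | 28.8% | 28.3% | 0.5 | 43.3% | 42.1% | 1.2 |
| 80% | 26.1% | 25.2% | 0.9 | 39.6% | 37.4% | 2.2 |
| 70% | 23.3% | 22.0% | 1.2 | 35.7% | 32.7% | 2.9 |
| 60% | 20.3% | 18.9% | 1.4 | 31.5% | 28.0% | 3.4 |

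Excess is computed before rounding.

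**Step 2: absolute arm difference.** Take s = 0.8. With L the lung-cancer and O the other-cause hazard, CIF = L/(L+O) × (1 − exp(−(L+O)t)). On placebo, L = 0.8λ and O = 0.2λ. On canakinumab, L = 0.776 × 0.8λ and O = r × 0.2λ. Placebo minus canakinumab, in points:

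| r | 1−KM, 36 mo | CIF, 36 mo | 1−KM minus CIF | 1−KM, 60 mo | CIF, 60 mo | 1−KM minus CIF |
|---|---|---|---|---|---|---|
| 0.5 | 5.18 | 4.64 | +0.54 | 7.22 | 5.96 | +1.26 |
| 1 | 5.18 | 5.01 | +0.17 | 7.22 | 6.86 | +0.36 |
| 1.5 | 5.18 | 5.36 | −0.18 | 7.22 | 7.72 | −0.50 |
| 2 | 5.18 | 5.71 | −0.53 | 7.22 | 8.55 | −1.33 |

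The sign changes with r.

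**Step 3: no lung-cancer effect.** With a lung-cancer hazard ratio of 1, the 1−KM difference is 0 for every r. The 60-month lung-cancer CIF difference runs from −1.08 points (r = 0.5) to +2.03 (r = 2). Lung-cancer CIF on its own can therefore mislead as well, which is why both causes must be shown together.

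**Step 4: the Cox hazard ratio.** In a simulation (60 runs, 1500 subjects, true ratio 0.776, other-cause deaths censored), the Cox hazard ratio was 0.775, 0.774 and 0.782 for r = 0.5, 1 and 2. It is not moved by the other-cause rate when causes are independent.

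**Step 5: which horizon applies.** Protocol 10.8 places the final DFS analysis, the basis of the primary report, 42 months after first randomization, so nobody would then have 60 months of follow-up. The final OS analysis was planned at 63 months. The close-out SAP says the primary endpoint was not met and sets a cut-off of 7 February 2023. The amendment log counts 507 subjects randomized by 5 February 2020, 36 months before that date, out of 1382 in all (507/1382 = 37%). It counts 63 by 11 December 2018, about 50 months before. The 36-month column is therefore the realistic one; the 60-month column is close to an upper limit.

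**The case against.** The best case for leaving the plan alone has four parts.

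- **The between-arm measure is sound.** Censoring competing deaths is the standard way to estimate a cause-specific hazard ratio. This stands.
- **The competing deaths are not hidden.** A reader might infer that a shift of deaths from lung cancer to infection could pass unseen in the LCSS output. SAP 2.7.1 contradicts that: censoring reasons and death cause are summarized by arm, and SAP 2.8.2 tabulates all deaths. These are counts without timing, though, and do not correct the curve or the median.
- **The direction is not fixed.** A reader might infer that Kaplan-Meier inflates the canakinumab benefit when other-cause death differs by arm. Step 2 does not support that. With sufficiently more other-cause death on canakinumab, the direction the infection signal suggests, Kaplan-Meier understates the difference relative to cumulative incidence. Step 3 shows that under independent causes extra infection deaths alone create no apparent LCSS gain in Kaplan-Meier, whereas lung-cancer cumulative incidence shown alone would suggest one.
- **The consequence is limited.** LCSS carries no alpha, OS counts every death, and the larger figures need long follow-up. Under the Step 1 model the Kaplan-Meier LCSS median is 66/s, so 66/0.6 = 110 months at a 60% share. A reader might cite that as a striking distortion, but it is well beyond this trial's follow-up and the median would most likely be not reached.

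These points remove any claim of a biased comparison or a concealed harm, and they make outright removal of Kaplan-Meier debatable. They leave untouched that the plan's only absolute LCSS estimate is biased upward when read as a risk.

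**Conclusion.** The concern holds in a limited form. As planned, 1−KM for LCSS overstates the absolute risk of lung-cancer death: by about 0.5 to 1.4 points at 36 months and 1.2 to 3.4 points at 60 months in the placebo arm, for assumed lung-cancer shares of 90% down to 60%. Absolute arm differences can be off in either direction: at an 80% share, by about half a point at 36 months and up to about 1.3 points at 60 months if the other-cause hazard is halved or doubled on canakinumab. The Cox hazard ratio is valid as a cause-specific measure.

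The sizes rest on constant, independent hazards, the plan's 66-month median, and assumed cause shares and other-cause ratios. The arm differences also borrow the OS hazard ratio. The direction of the overstatement needs none of these values; it follows from any other-cause death occurring. The readable text describes no adjudication of cause of death, so misattribution is a further uncertainty that neither estimator removes.

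**What to change.** In SAP 2.7.1:

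- Add Aalen-Johansen cumulative incidence of lung-cancer death, with other-cause death as the competing event, by arm with 95% confidence intervals at the yearly time points that follow-up supports.
- Show cumulative incidence of other-cause death beside it, so that a fall in lung-cancer death can be told apart from displacement by other causes.
- Label the stratified Cox result as the cause-specific hazard ratio.
- If the Kaplan-Meier curve is kept, state that it is a net, hypothetical quantity and not an absolute risk.

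The cost is SAP wording and one extra output from a standard procedure. Cause of death is already needed to derive LCSS, so no new data are required. The absolute figures will differ slightly from conventional Kaplan-Meier output.
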